### **Potential Risks/Discomforts:**

As any new investigational device, there are some risks. Some of potential risks could be:

- \* Skin related discomfort, such as tingling
- \* Skin reaction to adhesive patch

If the tingling sensation is too intense for the participant, they have the ability to reduce the intensity for their best level of comfort.

Some of the study devices (LegSys, SensiLase, PAMSys, and Tennant Biomodulator®) and technology are completely non-invasive, safe, non-toxic and non-ionizing. The potential risks are minimal. However, like any battery powered systems, there is a minimum risk of sensor malfunctioning. In addition, the study devices are not waterproof, and although they use a low powered battery (similar to a cell-phone battery), in order to avoid any risk of shock the monitor should not be submerged or saturated with fluids during operations or cleaning. Participants will be instructed to remove all devices before showering or going swimming.

Participants will be instructed that while receiving the in-home therapy, they should be lying or sitting down with their foot elevated. They will be instructed to not walk or perform other activities while receiving therapy.

A vibration perception device will be used to monitor progress and diagnose severity of peripheral neuropathy in lower extremities. The vibration range will be from 0-50 Volts. Participants may feel slight discomfort from the vibration. This device is compliant with medical electrical device safety according to IEC 60601-1.

There is a minimal risk of interference from the Tennant Biomodulator® in the functionality of pacemaker/ICD devices. Therefore, to avoid any adverse events, it is recommend avoiding the use of this device on subjects with a pacemaker/IDC.

The safety of electro-stimulation devices for use during pregnancy, birth or while nursing has not been established. We will be excluding potential subjects with these conditions.

Subjects must be willing to change the batteries of the device. Otherwise, they will not receive benefit from treatment. The study coordinators will provide batteries at every visit to the participant for the study device.

Since personal information is obtained, there is a possibility for invasion of privacy. These risks are considered minimal as they have a low likelihood of occurrence. Confidentiality will be maintained by storing the data for analysis without names attached, using a numerical code. All written data will be stored in a locked filing cabinet. A master list will be kept separately to facilitate follow-up data collection. Subject identifiers will not be included in any computer files. Only staff with the permission of the PI will have access to the master list linking names to code numbers. All staff will be made fully conversant with relevant ethical principles, particularly around confidentiality. These procedures are expected to be highly effective in protecting subject confidentiality.

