## Study Design

We are proposing a clinical study at the Baylor College of Medicine, Division of Vascular Surgery and Endovascular Therapy, to test the efficacy of daily home use of a novel electrical stimulation platform named the Tennant Biomodulator designed by AVAZZIA to accelerate wound healing, relieve pain and improve mobility in people with diabetes and non-infected plantar ulcers or wounds. In addition, we will examine immediate benefit of electrical stimulation provided by the Tennant Biomodulator on increasing skin perfusion. Our specific aims are:

**Aim1: Examine immediate benefit of lower extremity electrical stimulation to improve tissue perfusion (short term benefit):** We will recruit 40 eligible subjects (see table I for eligibility criteria). They will receive lower extremity electrical stimulation (at the shin level) for duration of approximately one hour using the Tennant Biomodulator Pro device. Skin perfusion before, at mid-point (approximately 30 min) and at the end of therapy will be measured. Skin perfusion will be assessed by Skin Perfusion Pressure (Sensilase, Vasamed Inc, MN, USA) and Kent Imaging. Other modalities such as HyperView Imaging (HyperMed Imaging, Inc., TN, USA) may be also used as comparator. Our hypothesis is:

*H1:* One-hour use of lower extremity electrical stimulation therapy will increase tissue perfusion.

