**Aim2: Examine long-term benefit of daily home use of lower electrical stimulation (long-term benefit):** Eligible participants will be randomized (ratio: 1:1) to either active (active group, n=20) or sham (sham group, n=20) therapy group. After receiving education, both groups will receive a home-based electrical stimulation system (Tennant Biomodulator device) for daily use at home up to 4 weeks. The duration of each treatment session per day will be one hour. The active group will receive an active electrical stimulation device. The control group will receive an identical device but without active electrical stimulation output. Participants and physicians who are treating the wound would be blinded to the type of device assignment. The study coordinator will be aware of assignment (active device or sham device). Each unit will be coded with a unique identification number. At the last visit, the study coordinator will reveal their group allocation. Since participating patients will have moderate-to-severe peripheral sensory neuropathy, they will be unable to determine via “feeling” whether or not they were receiving electrical stimulation. Patients will visit the clinic on weekly basis up to 4 weeks for assessing outcomes. The primary outcomes include changes in speed of wound healing and changes in plantar sensation. Secondary outcomes include patients self-report outcomes (e.g., pain, sleep quality, and quality of life), changes in mobility (e.g. physical activities and gait), and adverse outcomes (e.g., infection, amputation, etc.). Skin perfusion will be assessed similar to the method described in the Aim 1. Plantar sensation will be assessed using vibratory

perception threshold. Balance will be assessed using wearable sensors (BalanSENS, Biosensics LLC, MA, USA), mobility will be assessed using wearable sensors (PAMSys, Biosensics LLC, MA, USA), sleep quality will be assessed using PSQI questionnaire, and quality of life will be assessed using PROMIS Global.

Our hypotheses are

*H2:* Weekly speed of wound healing would be higher in the active group compared to the shame group

*H3:* Plantar sensation is improving in the active group in response to active therapy.

*H4:* Patient-reported outcomes and other secondary outcomes will be improved in the active group.

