- K162392 clearance for BEST-AV1 family of microcurrent devices with LED display for pain relief including reaction technology for Over-the-Counter use. They have the same output specifications and technology. The difference between Rx and OTC labeling is indication for use for temporary relief of pain associated with sore and aching muscles in the shoulder, waist, back, back of the neck, upper extremities (arm), and lower extremities (leg) due to strain from exercise or normal household work activities

The professional device with the LCD display will be used in the clinic, and patients will be issued the simpler device for home use.

*Tennant Biomodulator PRO® designed by AVAZZIA*

[figure not shown]
The candidate Tennant Biomodulator PRO® and the Tennant Biomodulator® devices designed by AVAZZIA are microcurrent transcutaneous electro-stimulation device with proprietary frequency sets specified by [name] MD within the BEST platform control options. The devices are easy-to-use, handheld, AA battery-operated portable device for use in the home or clinic. They apply charge and power to the tissue through electrodes where maximum power delivered to the load is controlled and limited, and an automatic shut off is implemented. The user can passively place the electrodes where indicated and apply stimulation for a period of time. The user controls the output by selecting the preset mode and power setting. The device's controls and visual indicators are located on the upper side of the case and on the upper cover.

Both Tennant Biomodulator® devices designed by AVAZZIA are indicated for:

- symptomatic relief and management of chronic, intractable pain
- adjunctive treatment in the management of post-surgical and post-traumatic pain

Tennant Biomodulator PRO® device	Tennant Biomodulator® device
 
The image shows the Tennant Biomodulator PRO device. It has a blue and black casing with a small LCD screen at the top displaying '3 13:17 TEN-8'. Below the screen are several control buttons and the AVAZIA logo at the bottom.
	 
The image shows the Tennant Biomodulator device. It has a black casing with a large LED display area. The display shows a blue and white graphic with a path of colored dots and labels for 'POWER' and 'MODE'. Below the display are four mode options: Assess, Ten-8™, Infinity, and Automatic. The AVAZIA logo is at the bottom.

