## Study Tasks:

Medical History: The presence of diabetes will be determined based on American Diabetes Association criteria. This will include: duration and type of diabetes, type of diabetes medication (insulin, oral, combination therapy, diet), previous history of foot ulcers, amputation (toe, foot), lower extremity bypass, lower extremity angioplasty, Coronary artery bypass surgery, cardiac angioplasty, arthritis, liver disease, osteoporosis, malignancy, and bone tumors. We will measure height and weight to determine body mass index (BMI). We will evaluate glycated hemoglobin, albumin and prealbumin at baseline. We will confirm PAD by measuring ABI.

Social Factors: We will evaluate the following factors: marital status, years of education, type of work, tobacco history (pack years, current smoker, current use of chewing tobacco, previous smoker, no tobacco history), drug history (current, previous history, or no history), and alcohol history.

BEST Therapy: The participant will be given an active Tennant Biomodulator PRO ® by the research staff. They will place the pads on the plantar area of the foot and provide therapy for one hour. At the end of the visit, the research staff will provide an active or sham Tennant Biomodulator ® to the participant for in-home therapy. The participant will have the ability of increasing/decreasing the intensity of the therapy with the Tennant Biomodulator ®. At each visit, the research staff will provide AA batteries to the participant for the device.

Peripheral Neuropathy: Neuropathy and its severity will be assessed using vibratory perception threshold (VPT) at the affected side. VPT will be evaluated at the distal great toe and fifth metatarsal head using a Biothesiometer.

Vascular Assessment: We will assess perfusion of the macro-circulation with arterial Doppler studies and microcirculation with Skin Perfusion Pressure measurements (SPP) at the affected side. We will use the SensiLase system (Väsamed) to measure SPP in mmHg. Ankle Brachial Index (ABI) will be also measured in the case of compressive vessel and if it was feasible (e.g. in non-hemodialysis patients) on the affected side. Additionally, we will use HyperView Imaging (HyperMed Imaging, Inc., TN, USA) or Kent Camera (Kent Imaging Inc., Calgary Canada) for surface tissue oximetry measurement.

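### Felt tingling is the only cue given to participants for over-intense home stimulation, although the protocol says they cannot feel whether it is on, and no task requires a look at the skin under the pads

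*Protocol*

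**What the plan says.** **Response to excessive stimulation.** Potential Risks/Discomforts (Protocol) names tingling and "Skin reaction to adhesive patch" as risks. For over-strong output it says: "If the tingling sensation is too intense for the participant, they have the ability to reduce the intensity for their best level of comfort". No other participant action is given for that case.

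**Ability to feel the output.** Study Design, Aim 2, argues for the blind as follows: "Since participating patients will have moderate-to-severe peripheral sensory neuropathy, they will be unable to determine via" sensation whether they are being stimulated. Randomization & Blinding repeats the argument and adds that participants have no earlier experience of such stimulation.

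**Home use.** Under Study Tasks, BEST Therapy, "The participant will have the ability of increasing/decreasing the intensity of the therapy". Aim 2 sets daily use for up to 4 weeks: "The duration of each treatment session per day will be one hour".

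**Pad site.** Aim 1 says "They will receive lower extremity electrical stimulation (at the shin level) for duration of approximately one hour". The BEST Therapy task, describing the clinic session, says "They will place the pads on the plantar area of the foot and provide therapy for one hour". No separate site is given for home use.

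**Protections in place.** Study Device states that "maximum power delivered to the load is controlled and limited, and an automatic shut off is implemented". It also says that the displays show the power setting and an indication of tissue reaction. The Schedule of Events marks adverse-event reporting at baseline and at each weekly visit.

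**The concern.** A safeguard that depends on sensation does not work in people who lack the sensation. The protocol relies on absent feeling to protect the blind and on present feeling to limit the intensity. The same participant cannot supply both.

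The second gap concerns recording. The protocol names a skin reaction as a foreseeable risk but does not ask anyone to look for it. These are people with diabetes and an existing foot or leg wound, and the Background itself says that wounds below an arterial perfusion defect may fail to heal. Skin damage that goes unnoticed therefore matters more here than in a general pain population. Adverse outcomes are also a listed secondary outcome. A report of no skin reactions is reassuring only if the skin was examined and the finding written down.

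**Working it through.** No arithmetic applies. The plan states no figure on this point, so the check is a comparison of texts.

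1. **Is felt tingling the only participant-level cue?** Potential Risks/Discomforts gives that cue alone. The BEST Therapy task gives the control (intensity up or down) but no other reason to use it and no maximum setting for the participant. Study Device describes a visible power setting and tissue-reaction indicator, so a participant can see the level without feeling it. No section names a setting or reading at which to turn the device down. As an instruction to act, felt tingling is the only one stated.

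2. **Can participants be expected to feel it?** Study Design, Aim 2, and Randomization & Blinding both say no. Table I does not require neuropathy, so some participants may in fact have sensation.
   - If a participant cannot feel the output, the tingling cue fails for that person.
   - If a participant can feel it, the cue works, but the stated reason for the blind does not hold for that person.

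   The two statements cannot both be relied on for the same person. How many participants fall on each side cannot be derived from the documents.

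3. **Does any scheduled task examine pad-contact skin?** These are the entries of the Schedule of Events and Study Tasks that come nearest:

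| Entry | Stated target | Pad-contact skin required? |
|---|---|---|
| Wound photos | size of the wound | No |
| Thermal images | inflammation at the wound | No |
| WIfI classification | the wound and limb | No |
| Wound care | standard care (baseline and two follow-ups, as extracted) | No |
| BEST Therapy in clinic | pad placement and one-hour session | No, though the skin at the clinic site is exposed |
| Adverse-event reporting | events in general | No specific item |
| Phone interview | events after the visits | No |

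   Staff have several chances to see the foot, but none of these entries tells them to inspect the pad site or to record that it was clear.

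4. **Would staff know where to look?** The documents give the shin in one place and the sole in another, with no home site. If the home pads go on the shin, wound photos and plantar pad placement in clinic need not show the relevant skin.

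**The case against.** The strongest reply is that the tingling sentence manages comfort, not injury: someone who feels nothing has no discomfort to relieve, and someone who does can turn the device down. Protection against harmful output comes from the power limit and shut-off, which need no sensation. The device family is also cleared for over-the-counter use at the same output specifications. The displays make the setting visible. Pads are applied in clinic at the visits, a willing participant or caregiver handles dressings and stimulation, and a skin reaction that is seen can be entered as an adverse event. The adverse-event form and the content of the participant education are not in the documents, and consent pages were removed. Any of these may already contain a skin check.

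Much of this stands and keeps the point small. It does not remove it. The over-the-counter indication is for sore muscles, not for insensate feet with ulcers. The displays are described without any instruction tied to them. An opportunity to see the skin is not the same as a recorded look.

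A reader might infer that unfelt high settings will injure participants. The documents do not support that: nothing in them shows harm from output within the device limit, or that an adhesive reaction depends on intensity. A reader might also infer that the comparison of adverse events between arms is biased. That does not follow either. The sham is identical apart from output, so an adhesive reaction can occur and be missed in either arm.

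The fix also has a fair objection against it. If output causes visible redness, a weekly check could hint at allocation, which is why it matters who does the check.

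**Conclusion.** The point holds as a minor safety point with a cheap improvement. The participant-level safeguard does not work in the population the protocol describes, and a named skin risk has no required look attached to it. Device limits, visible indicators and adverse-event reporting at each visit reduce the risk.

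No numerical size can be given. The documents contain no reaction rate, no share of reactions that would be noticed unprompted, and no count of participants without sensation. An upper limit computed from an assumed count of zero would be the same for any trial of 40 people, so it would say nothing about this one.

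The conclusion rests on two assumptions: that the adverse-event form and participant education do not already include a pad-site check, and that at least some participants have the neuropathy the protocol attributes to them. If the form already has skin items, most of the recording gap closes.

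**What to change.** 1. **Pad site.** State where the pads go at home, and reconcile the shin wording in Aim 1 with the plantar wording in the BEST Therapy task.
2. **Potential Risks/Discomforts.** Add that the participant or caregiver looks at the pad site each time the pads are removed and reports redness, blister or broken skin. Keep the tingling sentence for those who can feel it. No intensity or dose rule is needed.
3. **Weekly visits.** At each existing visit, before any stimulation in clinic that day, check pad-site skin in both arms and record redness, blister and broken skin as present or absent. The checker should preferably be blinded and not be the person who measures the wound. If only the unblinded coordinator is available, take a pad-site photo alongside the wound photo and have it read blind to arm.
4. **Analysis.** Report these prompted items descriptively by arm, separate from the chi-square comparison of adverse events in the Protocol's Statistical analysis section, so that solicited findings do not alter that test.

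If follow-up is already complete, the report should say that pad-site skin was not systematically examined, unless the adverse-event form shows that it was.

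**Cost.** Two wording changes, three tick-box items and about a minute per visit (an assumption): 4 follow-up visits × 40 participants × 1 minute = 160 minutes over the trial. A blind photo read, if used, might add about another minute each (also an assumption). No new visit or test is needed. The downside is a small chance that visible redness hints at allocation, and the choice of checker limits this.

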**Potential Benefits:**

There may be no direct benefit to the participant by being in this study. However, the information that will be gathered and analyzed from this research may help in development of a useful adjunct therapy program to improve wound healing and patient-centered outcomes including as pain and mobility among people with diabetic foot ulcers. It is part of a larger prevention initiative to reduce the high number of traumatic amputations associated with the diabetic foot disease.

The body of work in this area suggests opportunities for better patient care using a simple, inexpensive approach that has few adverse effects. There is a possibility of improving speed of wound healing and reducing associated pain.

### **Subject compensation:**

Participants will be compensated with \$50 per visit. For five completed visits a total of \$250 may be compensated to the subject. We will be also providing parking validations.

**Title: ELECTRICAL STIMULATION AS AN ADJUNCTIVE THERAPY TO ACCELERATE WOUND HEALING
IN PEOPLE WITH PERIPHERAL ARTERIAL DISEASE AND PLANTAR ULCERS & A RANDOMIZED
CONTROLLED TRIAL**

Identifier: NCT03821675

Date: 10/8/2021

Statistical analysis plan

Continuous data were reported with mean \pm standard deviation (SD). Categorical data were presented as count (%). Shapiro-Wilk test was conducted to identify the normal distribution of continuous variables. One-way ANOVA for normally distributed variables or Mann-Whitney U test for non-normally distributed variables was used to estimate differences of mean between control and intervention groups. χ^2 test was used to determine significant level between the groups for categorical variables. The effect size was measured using OR and 95% CI for categorical variables, and Cohen's d to discriminate the difference of primary and secondary outcomes between groups. Outcome changes were assessed over time compared to BL within (ie, time effect) and between (ie, time \times group effect) groups using linear mixed model for normally distributed outcome and generalized estimating equations for non-normally distributed outcome with adjustment for potential confounders. Least significant difference method was used for multiple pairwise comparisons. Pearson and Spearman correlation analysis were performed to assess the relationship between wound or demographics/clinical characteristics, and vascular outcomes. The level of statistical significance was set at $P < .050$. To detect changes in perfusion in individuals with marked limb ischemia, a sub-analysis of patients with moderate to severe peripheral arterial disease (PAD) (ABI < 0.8 or > 1.4 at BL)²⁴ was performed. To detect associated risk comorbidities influencing wound healing in those healers (defined as $\geq 50\%$ of area reduction)²⁵ vs non healers under E-stim, a sub-analysis in the IG was also performed.

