### **Sample size estimation:**

The estimated number of study subjects is 40. The sample size for the short-term effect (immediate changes in skin perfusion) was estimated to achieve 85% power when comparing to baseline values, using assumed rates of 50% and 10% improvement, respectively. A two-sided test of results in evaluable subjects (qualified for analyses of efficacy on immediate changes on skin perfusion) will provide the specified power at a 5% significance level. Sample size calculations resulted in a requirement for a total of 27 subjects. The sample size for long term benefit was estimated based on our previous study (Najafi et al, Diabetes Sci & Tech, 2017) in which effectiveness of daily use of electrical stimulation to improve balance was examined using a randomized controlled trial model. An effect size of greater than Cohen’s  $d=1.35$  was observed for improvement of mobility post plantar electrical stimulation intervention. In this study we will use a power of 80%, two –tailed t-test, and alpha level of 5% to observe a significant improvement in the intervention group receiving active stimulation compared to sham group (with nonfunctional stimulator), 18 subjects per group is required. Assuming a 10% drop out, the estimated sample size would be 20 subjects per arm. We recognize that this sample size may not be sufficient to validate all primary and secondary outcomes, but would be sufficient to estimate trend and estimate the sample size for follow up study. Upon approval of the sponsor, availability of budget, and based on initial results (first 20 subjects), the sample size may be increased as well.

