### **Statistical analysis:**

Continuous variables are expressed as mean +/- standard deviation (SD). Unpaired t-tests, Mann-Whitney U-tests, and Chi-square-tests will be used for baseline comparison according to the scale of the investigated variable and the distribution of the data. Repeated measures ANOVA tests will be used for examining the effect of intervention in each group after adjusting by age and BMI. Similar test will be used for short-term effect (i.e. changes in skin perfusion immediately after electrical stimulation) and long term benefit (i.e. changes in primary and secondary outcomes after 4 weeks). To account for missing data (prevent entire subject data removal due to lack of a data point), a linear mixed-effect model will be selected instead of univariate general linear model repeated measures analysis. T Chi-square-test will be used for comparing the incident of AE between groups. The effect size to discriminate between groups will be estimated using Cohen's *d* effect size and represented as *d* in the results section. Values ranging from 0.20 to 0.49 indicate small; from 0.50 to 0.79 indicate medium, from 0.80 to 1.29 indicate large, and above 1.30 indicate very large effects. Values less than 0.20 are considered as having no noticeable effect. Spearman correlation of coefficient will be used to examine association between changes in motor parameters and changes in skin perfusion and plantar sensation post intervention. All analyses will be performed using SPSS statistics (version 24; IBM, Armonk, NY, USA) , with a significance level of  $p < 0.05$ .

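### Adverse outcomes get no planned interval for a proportion or an absolute difference; the only named categorical effect measure, the odds ratio, breaks down when an arm of 20 has no events

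*SAP*

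**What the plan says.** The SAP summarises categorical data as counts and percentages, compares groups by chi-square, and names a single effect measure: "The effect size was measured using OR and 95% CI for categorical variables". It gives no rule for cells with zero events, no exact test, no interval for a single proportion and no risk difference. It does not mention infection, amputation or adverse events by name.

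The protocol (Study Design, Aim 2) makes "adverse outcomes (e.g., infection, amputation, etc".) secondary outcomes. Its Statistical analysis section gives one method for adverse events: "Chi-square-test will be used for comparing the incident of AE between groups". No effect estimate is attached to that test.

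Participants are to be "randomized (ratio: 1:1) to either active (active group, n=20) or sham (sham group, n=20) therapy group". Under Sample size estimation, the long-term aim states that "18 subjects per group is required", and then: "Assuming a 10% drop out, the estimated sample size would be 20 subjects per arm". Neither document gives an expected event rate, or a power or precision target, for any adverse outcome.

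**The concern.** Infection, amputation and the occurrence of an adverse event are yes/no outcomes, so the SAP's general sentence on categorical variables appears to govern them. With 20 people per arm, one arm may have no events. The sample odds ratio is then zero or infinite and its standard (Wald) interval does not exist. If neither arm has an event, the odds ratio is undefined.

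In those cases the plan leaves counts, percentages and a low-powered p-value. A reader cannot see how large a difference in harm the data still allow, and may take non-significance as reassurance. The protocol says that the trial may be too small for all its outcomes and presents it as a way to see trends and to size a follow-up study. For that purpose, absolute rates and differences with intervals are the useful output.

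**Working it through.** **Inputs.** 20 per arm (Protocol, Study Design and Sample size estimation); 18 per arm if the planned 10% drop out. Event rates are **assumed**, from 2% to 20% for the failure of the odds ratio and up to 30% for power, because the documents give none.

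**The plan's own figure.** 18 / (1 − 0.10) = 20, so the drop-out step reproduces. How the 18 was reached does not matter here; the check needs only the arm size.

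**How often the plain odds ratio fails.** With the same true rate p in both arms and n per arm, an arm is empty with probability (1 − p)^n. So P(at least one arm empty) = 1 − [1 − (1 − p)^n]², and P(both empty) = (1 − p)^(2n).

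Example, p = 5%, n = 20: 0.95^20 = 0.358; 1 − (1 − 0.358)² = 0.588; both empty 0.358² = 0.129.

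| Assumed rate, both arms | One arm empty (n = 20) | Both empty (n = 20) | Plain OR fails (n = 20) | Plain OR fails (n = 18) |
|---|---|---|---|---|
| 2% | 44% | 45% | 89% | 91% |
| 5% | 46% | 13% | 59% | 64% |
| 10% | 21% | 1.5% | 23% | 28% |
| 15% | 7.5% | 0.2% | 8% | 10% |
| 20% | 2.3% | about 0% | 2% | 4% |

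With unequal rates and n = 20, it fails in 38% of trials at 5% v 15% and in 12% at 10% v 30%.

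**What can still be estimated when one arm is empty (n = 20).**

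| Events | Sample OR | Conditional exact 95% CI | OR with +0.5 per cell (95% CI) | Risk difference (Newcombe 95% CI) |
|---|---|---|---|---|
| 0 v 2 | infinite | 0.19 to infinity | 5.5 (0.25 to 123) | 10 points (−8 to 30) |
| 0 v 3 | infinite | 0.43 to infinity | 8.2 (0.40 to 170) | 15 points (−4 to 36) |

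For one empty arm, the exact two-sided 95% upper limit is 1 − 0.025^(1/20) = 16.8%. This limit is available for each arm even when both are empty.

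**The test.** Exact enumeration at 20 per arm, two-sided 5%, gives this power:

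| True rates | Chi-square, uncorrected | Fisher |
|---|---|---|
| 5% v 15% | 15% | 7% |
| 5% v 20% | 29% | 17% |
| 10% v 30% | 36% | 24% |

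With equal arms the expected number of events per arm is half the total, so it is below 5 whenever there are 9 events or fewer. The choice of test can then change the conclusion. For 0 v 4 of 20, the expected count is 2 per arm and chi-square = 40 × (20 × 4)² / (20 × 20 × 4 × 36) = 4.44, p = 0.035. Fisher gives p = 0.106. Fisher is significant only from 0 v 5 (p = 0.047).

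**The case against.** Several stronger readings are tempting, and the documents do not support them.

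- **That the SAP assigns the odds ratio to infection, amputation and adverse events.** It does not name them. The sentence is general and could also serve baseline characteristics or healer status. Its application to harms is an inference from that sentence and the protocol's list of secondary outcomes. It is a fair inference, since nothing exempts harms, but it should be stated as one.
- **That safety would rest on a p-value alone.** The SAP also reports counts and percentages. What is missing is an interval around the proportions and around their difference.
- **That the odds ratio will often be incomputable.** This depends on rates that the documents do not give. The protocol describes device risks as minimal, treatment lasts 4 weeks, and infection, osteomyelitis and gangrene are excluded at entry, all of which point to low rates for some events. But skin discomfort and patch reactions are listed as risks, and a phone interview at 12 weeks also records adverse events. All adverse events pooled could be well above 5%.
- **That no interval would exist.** With one empty arm, a conditional exact or +0.5-corrected interval can be calculated, and the SAP does not rule these out. It does not name them either, and they say little.
- **That the trial plans to claim equal safety.** No text proposes this, and the protocol admits that the sample may be too small. The low power comes from the sample size and would not be improved by another effect measure.

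It is also fair to say that a risk difference of −4 to 36 points is wide. But it is finite, and it shows the reader how much is unknown.

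**Conclusion.** The point holds in a limited form. The odds ratio is the only effect measure named for categorical variables, there is no sparse-data rule, and no interval is planned for a proportion or an absolute difference. At 20 per arm the plain odds ratio fails in more than half of trials if the true rate is about 5% or less, in roughly one in four at 10%, and seldom at 15% or more. These figures assume equal rates in both arms and independent participants. That harms fall under the SAP sentence is inferred.

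The chi-square test without an exact alternative is a related weakness: it is least reliable at the low event counts where the odds ratio also fails. The change should be made because a plainly better summary is available from the same counts. It concerns how harms are reported and does not touch the wound-healing or sensation analyses.

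**What to change.** **SAP.** For adverse outcomes, replace the odds ratio with the number of participants affected per arm (percentage and exact 95% CI) and the risk difference, active minus sham, with a Newcombe 95% CI.

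**Protocol, Statistical analysis.** There is no odds ratio here to replace. Add the same measures for adverse events beside the planned test.

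**Both.** Use Fisher's exact test instead of chi-square when any expected count is below 5. State that a non-significant result is not evidence of equal safety.

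**Cost.** A few sentences and no new data. The intervals will be wide and will look less favourable than a bare count. The exact test is more conservative: for 5% v 20%, power is 17% with Fisher throughout, against 29% with uncorrected chi-square.
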